## 18.0 Records and Data Collection Procedures

Baseline data will be entered  $\leq 10$  working days of patient registration. This will include patient ID, age, gender, tumor type, dose level, and baseline symptoms.

Cycle 1 toxicity data will be entered  $\leq 24$  hours after evaluation of the patient and  $\leq 10$  working days after evaluation on all other cycles.

Response status will be entered  $\leq 10$  working days of evaluation for response as defined by protocol.

Phase I only: Three months after the patient goes off treatment, follow-up information will be collected and entered. This includes off treatment, off study, survival, and death data. After 3 months have elapsed from off treatment date, no further follow-up is required (i.e., patient goes off study).

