## 4.2 Event Monitoring/Survival Follow-up

|                  | Event Monitoring Phase* |       |                         |       |                    |
|------------------|--------------------------------|-------|-------------------------|-------|--------------------|
|                  | Every 3 months until PD        | At PD | After PD every 6 months | Death | New Primary        |
| Event Monitoring | X                              | X     | X                       | X     | At each occurrence |

\*If a patient is still alive 2 years after registration, no further follow-up is required.

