#### 13.2 Progressive disease (PD)

Patients who develop PD while receiving therapy will go to the event-monitoring phase.

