#### 13.3 Off protocol treatment

Patients who go off protocol treatment for reasons other than PD will go to the event-monitoring phase per Section 4.0.

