#### 16.12 Sample Size

In the phase I portion, the study may involve as few as 6 patients (2 DLTs in Dose Level 1 and Dose Level -1) or as many as 12 patients (6 for each Dose Level). In addition, up to 37 patients will be treated at the recommended Phase II dose during the study (6 from phase I, 31 from phase II). Therefore, the maximum number of evaluable patients is 43 because the recommended Phase II dose will include 6 patients from the phase I portion. An additional 6 patients may be accrued to account for patients that need to be replaced bringing the maximum overall accrual to 49.

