#### 16.4 Phase II Statistical Design

- 16.41 Interim Analysis: In the expanded cohort part of the trial, 17 patients will be accrued (this will include the patients treated at the MTD from the phase I component). If 3 confirmed responses or less are observed in the first 17 eligible patients, then the trial will be terminated and the treatment deemed not worthy of further study. If at least 4 confirmed responses are observed among these 17 patients, then an additional 20 patients will be accrued to the second stage.
- 16.42 Final Analysis: If 11 or more confirmed responses are observed at the end of the trial in the first 37 eligible patients, the treatment will be considered promising. This design yields at least 90% probability of a positive result if the true response rate is at least 40%.
- 16.43 Over Accrual: If more than the target number of patients are accrued, the additional patients will not be used to evaluate the final decision rule or used in any decision making process. Analyses involving over accrued patients are discussed in Section 16.54.
- 16.44 Other considerations: Adverse events, quality/duration of response, and patterns of treatment failure observed in this study, as well as scientific discoveries or changes in standard care will be taken into account in any decision to terminate the study

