### 18.2 Event monitoring (Phase II only)

See [Section 4.0](#) and data submission table for the event monitoring schedule.

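### Section 18 ends follow-up of Phase I patients 3 months after treatment, while Sections 4.2, 13.2 and 13.3 run to death or 2 years; Phase II overall survival is exposed through the Phase I patients counted in it

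*Combined protocol and SAP*

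**What the plan says.** Two sets of instructions cover what happens after a Phase I patient stops treatment.

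- **Short follow-up.** Section 18.0, in a paragraph marked for Phase I, collects off-treatment, survival and death data at 3 months and then states: "After 3 months have elapsed from off treatment date, no further follow-up is required (i.e., patient goes off study". Section 18.2 is headed "Event monitoring (Phase II only)".
- **Long follow-up.** Section 4.2 schedules contacts every 3 months until progression and then "After PD every 6 months", with deaths recorded. Its end point is: "If a patient is still alive 2 years after registration, no further follow-up is required". Section 13.2 says: "Patients who develop PD while receiving therapy will go to the event-monitoring phase". Section 13.3 says: "Patients who go off protocol treatment for reasons other than PD will go to the event-monitoring phase per Section 4.0". None of these three sections mentions phase.

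Some Phase I patients also belong to the Phase II sample. Section 16.12 makes up the 37 patients as "6 from phase I, 31 from phase II", and Section 16.41 says of the first 17 that "this will include the patients treated at the MTD from the phase I component". Section 16.622 counts them in the Phase II adverse-event stopping rule as well.

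OS is a Phase II secondary goal (Section 2.24), measured from registration and estimated by Kaplan-Meier (Section 16.522). Section 16.52 does not say which patients form the OS analysis set.

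**The concern.** A site with a Phase I patient off treatment has two incompatible instructions. Under Section 4.2, contact after progression comes at 6-month intervals. Under Section 18.0, the same patient has left the study before the first of those contacts.

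If Section 18.0 is followed, two follow-up rules operate inside one 37-patient cohort. The Phase I members are censored for OS 3 months after stopping treatment. Progression is the first stopping reason listed in Section 8.3, so this censoring tends to remove patients whose risk of death has just risen. Kaplan-Meier then treats them as having the average risk of those still followed, and the OS estimate drifts upward. The exploratory OS analysis of Phase I in Section 16.33, overall and by dose level, is cut short in the same way.

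**Working it through.** **1. Who is affected.** From Sections 16.12 and 16.41: 6/37 = 16.2% of the full Phase II sample. If the trial stops at stage 1, it is 6/17 = 35.3%, but OS drives no decision there. Six is a ceiling.

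**2. The two rules for one patient.** Suppose a Phase I patient progresses at the first scan (6 weeks, Section 11.1) and stops treatment.

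| | Section 18.0 | Sections 4.2 and 13.2 |
|---|---|---|
| Last required contact | 1.5 + 3 = 4.5 months | death or 24 months |
| First routine contact after progression | none after 4.5 months | about 1.5 + 6 = 7.5 months |

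**3. Deaths missed: simple check.** Section 1.1 puts survival in advanced NSCLC at about 1 year. Assume exponential OS with a median of 12 months.

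- Expected deaths by 24 months among six patients: 6 × (1 − 0.5^(24/12)) = 4.5.
- With treatment ending at 3 months and censoring at 6 months: 6 × (1 − 0.5^(6/12)) = 1.8 seen, so 2.7 missed.
- With treatment ending between 1.5 and 9 months, 1.5 to 3.1 of the 4.5 are missed.

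**4. Deaths missed: separating time on treatment from survival afterwards.** The documents give neither figure, so these are assumptions: exponential time on treatment T (median 3, 4 or 6 months), exponential survival afterwards S (median 6 or 8 months), and 0% or 10% of patients dying as treatment ends. A death within 24 months goes unrecorded when S > 3 and T + S ≤ 24. With no deaths as treatment ends, the probability is exp(−3b) × F(21), where b = ln 2 / (median of S) and F is the distribution function of T + S.

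For medians of 4 and 6 months:

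- exp(−3b) = 0.5^(3/6) = 0.707; F(21) = 0.787; F(24) = 0.844.
- Unrecorded: 0.707 × 0.787 = 0.557 of patients, and 0.557/0.844 = 66% of deaths within 24 months.
- Among six patients: 6 × 0.844 = 5.1 deaths, of which 6 × 0.557 = 3.3 are unrecorded.

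Over all settings, 57-72% of these patients' deaths within 24 months are unrecorded, which is 43-59% of the patients.

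**5. Bias in Kaplan-Meier OS.** Trials were simulated under the same assumptions. Six patients were censored at the earlier of 24 months and T + 3 months, the others at 24 months. Bias is the mean estimate minus the mean with full 24-month follow-up, over 12, 18 and 24 months.

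| Dying as treatment ends | 6 of 37 | 6 of 17 |
|---|---|---|
| 0% | 0.4 to 1.8 points | 1.2 to 4.2 points |
| 10% | 0.3 to 1.5 points | 0.9 to 3.6 points |

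For scale, the 95% half-width at 50% survival, ignoring censoring, is 1.96 × √(0.25/37) = 16.1 points, or 1.96 × √(0.25/17) = 23.8 points.

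**6. PFS.** A patient who stops for progression already has the PFS event, so only those who stop without progression matter. Assume a median PFS of 5 months and 10-30% stopping without progression. The 1-year PFS rate moves by −0.01 to 0.02 points if the hazard is unchanged after stopping. If it doubles, the shift is 0.10-0.26 points (6 of 37) or 0.23-0.59 points (6 of 17).

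**7. Primary endpoint.** Confirmed response is judged over the first 6 months of treatment (Section 16.11), so it is little affected.

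**The case against.** The strongest reply is that the sections can be read together. Sections 18.0 and 18.2 are labelled by phase and agree with each other, while Sections 4.2, 13.2 and 13.3 are merely silent. Specific text would then limit general text. That reading softens the contradiction but makes the early censoring certain, because nothing exempts the Phase I patients counted in Phase II.

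A second reading avoids the loss: if the Phase II label in Section 18.2 covers the MTD patients, as Section 16.622 does for adverse events, they would be event-monitored. That is possible, but Section 16.622 is a safety rule and Section 18 does not say so. Sections 18.1 and 18.2 also point to a data submission schedule that is not in the document and might settle the matter in practice.

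Several points stand as limits:

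- Survival up to 3 months after treatment is still collected, so OS is censored early and not lost outright.
- That the six patients enter the Phase II OS curve is an inference from Sections 16.12, 16.41 and 16.622. Section 16.33, which defers fuller exploration of OS and PFS to Phase II, is consistent with it but does not prove it.
- The size of the bias depends on the assumptions. With 20% or 30% dying as treatment ends, it falls to about 0.2-1.3 or 0.1-1.0 points at n = 37, still upward.
- The synopsis gives Phase I as 3 months (maximum 6), against 5-10 months in Section 16.13. On the shortest timetable the MTD would be known before any patient reached the 3-month limit.

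**Conclusion.** The concern holds. The follow-up rules for Phase I patients conflict, and on the plain reading of Section 18.0 up to 6 of the 37 Phase II patients are censored early and informatively for OS. Under the stated exponential assumptions, more than half of their deaths within 24 months go unrecorded, and OS at 12-24 months is overstated by about 0.3-1.8 points (0.9-4.2 points if only 17 patients are enrolled). This is well inside the sampling error. It bears on a descriptive secondary endpoint, with negligible effect on PFS and little on the primary endpoint. The plan should be corrected because the fix is cheap and survival data not collected at the time may not be recoverable. The conclusion about Phase II OS rests on the MTD patients being in that analysis set; the contradiction itself does not.

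**What to change.** Reconcile Sections 18.0 and 18.2 with Sections 4.2, 13.2 and 13.3. Suggested text:

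> Phase I patients treated at the MTD and counted in the Phase II sample follow the event-monitoring schedule of Section 4.2 until death or 2 years after registration. The 3-month rule applies only to Phase I patients not counted in Phase II. Until the MTD is declared, all Phase I patients remain on the Section 4.2 schedule.

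The last sentence is needed because a patient who stops at the first scan would be off study at about 4.5 months, while Section 16.13 allows 5-10 months for Phase I. It may not yet be known whether that patient will be counted.

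In Section 16.52, state whether the Phase I patients treated at the MTD belong to the OS and PFS analysis set, and align the data submission schedule with the revised text.

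Cost: two or three sentences, and status checks every 3 to 6 months for about 6 patients (up to 12 until the MTD is declared). No visits or procedures are added, and the sample size and decision rules do not change.

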### 18.1 Submission Timetable

Data submission instructions for this study can be found in the Data Submission Schedule.

### 18.2 Event monitoring (Phase II only)

See [Section 4.0](#) and data submission table for the event monitoring schedule.

### 18.3 CRF completion

This study will use Medidata Rave for remote data capture (rdc) of all study data.

### 18.4 Site responsibilities

Each site will be responsible for insuring that all materials contain the patient's initials, MCCC registration number, and MCCC protocol number. Patient's name must be removed.

### 18.5 Supporting documentation

This study requires supporting documentation for evidence of response to study therapy and progression after study therapy.

### 18.6 Labelling of materials

Each site will be responsible for insuring that all materials contain the patient's initials, MCCC registration number, and MCCC protocol number. Patient's name must be removed.

### 18.7 Incomplete materials

Any data entered into a form will result in that form being marked as "received." However, missing data will be flagged by edit checks in the database.

### 18.8 Overdue lists

A list of overdue materials is automatically available to each site at any time. A list of overdue materials and forms for study patients will be generated monthly. The listings will be sorted by location and will include the patient study registration number. The appropriate co-sponsor/participant will be responsible to submit the overdue material.

### 18.9 Corrections forms

If a correction is necessary the QAS will query the site. The query will be sent to the appropriate site to make the correction in the database and respond back to the QAS.

**19.0 Budget**

- 19.1 Costs charged to patient: Routine clinical care
- 19.2 Tests to be research funded: Research blood, ECG, Echocardiogram, Anetumab raptansine and the administration, biopsy costs, if necessary

